A.3. High-Deductible Health Plans in the US are Expanding at Unprecedented Rates [*RQ-5*]: The US has been grappling for decades with rising health spending, which outpaces inflation and is often cited as a threat to the economic sustainability of governments, employers, and families.²⁰ In response, payers²¹ and employers²² have increasingly turned to high-deductible health plans (HDHPs) with high levels of patient cost-sharing. Compared with traditional plans, HDHPs have lower monthly premiums, but they subject most services to annual deductibles of \$2,600 to \$12,900 per family.²³ Families might therefore pay the entire deductible amount out-of-pocket before more generous coverage, such as full coverage or coinsurance, begins.

Two types of HDHPs predominate in the US: Health Savings Accounts (HSA) eligible and HSA-ineligible HDHPs. The 2003 Medicare Modernization Act created HSAs that allow employers and employees to contribute tax-free funds into accounts for medical services payments.²⁴ Such accounts must be connected to HDHPs that have a regulated structure including minimum deductible amounts, maximum annual account contributions, and defined coverage requirements. HSA-eligible HDHPs with "value-based" out-of-pocket exclusions often fully cover a limited number of preventive services (e.g., cancer screening), have a moderate copayment (e.g., \$20) for annual primary care physician preventive visits, but require full cost-sharing up to the annual deductible for all other services (e.g., mental health visits, medications, tests, hospitalizations). In contrast, HSA-ineligible HDHPs (i.e., Health Reimbursement Arrangement plans or those without an associated account) are also designed to be "value-based," but generally include more generous drug coverage (i.e., relatively low medication copayments as in traditional plans) and specialist visits might be exempt from the deductible; most other services including mental health visits and hospitalizations are subject to the deductible.

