B.3. Pathways toward Improvements in Care [RQ-3]: HDHPs could cause disruptions in treatment of bipolar illness due to cost-related nonadherence or confusion about coverage details. HDHPs could also cause reductions in outpatient and inpatient care, or increased psychiatric hospitalizations due to treatment disruptions. Because of the rapid growth in HDHPs, our study is highly relevant to policymakers at all levels. Both types of HDHPs (with and without medications subject to the deductible) as well as traditional plans with no deductible are all highly prevalent in the US. This wide “practice variation” in insurance benefits design implies a crucial need to understand the impacts of design differences in order to optimize patient health. Prior research indicates that even small differences in insurance design can have powerful consequences for vulnerable patients.

Opportunities to implement policy recommendations would be readily available. Insurers redesign benefit offerings every year and respond quickly to shifting pressures from employers. Our study potentially includes an immediately-available “policy intervention,” if HDHPs with generous medication coverage promote bipolar medication adherence and better health outcomes, employers and health insurers could quickly shift to such designs. Evidence that exempting mood stabilizing drugs from full cost-sharing preserves appropriate utilization could also contribute to amendments to the 2003 Medicare Modernization Act that requires HSA-eligible HDHPs to subject all medications to the deductible.²⁴ State and federal regulators closely examine insurer practices and set standards for benefits packages. We expect that policy makers will use our results to introduce health plan designs that promote high quality care among patients with mental illness.

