To assess the efficiency of data linkage between claims data and credit report data and implications for bias based on proportion of total sample that may not have these data [IR-2], data vendor Optum will link patient addresses to geocoded 2000 and 2010 census data, a process that has previously yielded <1% unlinked data. Information on member race and ethnicity is also included, based on geocodes, US census data, and an imputation strategy incorporating member surname. [MD-2] We will also have detailed benefit information for ~80% of employers, including individual and family deductible levels, HDHP type (HSA, Health Reimbursement Arrangement, or non-account), and copay and coinsurance amount by service type. For employers with missing deductible levels, [MD-2] we have developed an imputation algorithm that has 97.0% sensitivity and 96.2% specificity. To determine employer deductible levels, we will use a benefits type variable that we have for smaller employers (with approximately 100 or fewer employees). For larger employers, we will take advantage of the fact that health insurance claims data are the most accurate source for assessing out-of-pocket obligations among patients who utilize health services. Our claims data contain an in-network/out-of-network deductible payment field. For patients who use expensive or frequent services, the sum of their yearly deductible payments will add up to clearly identifiable exact amounts such as \$500.00, \$1000.00, \$2000.00, etc. When several members have these same amounts, it provides strong evidence that the employer offered such an annual deductible level. It will also be possible to detect employers that offer choices of deductible levels when multiple employees have deductibles at two or more levels, such as 20 employees with an annual amount of \$1000.00 and 12 employees with \$500.00. For employers with at least 10 workers, we therefore will sum each employee's in-network deductible payments and number of claims over the enrollment year and plan to assess other key characteristics such as percentage with Health Savings Accounts. On a randomly selected half of the employer data set that contained our calculated employer characteristics (such as the percentage of patients with deductible levels between \$1000-\$2500) as well as actual deductible amounts, we will use a logistic model that predicts the 3-level outcome of deductible <=\$500/\$500-\$999/>\$1000 based on multiple aggregate employer characteristics such as the first and second most common whole number deductible value, the percentage with Health Savings Accounts or Health Reimbursement Arrangements, the median deductible payment, the percentage of employees using services, the employer size, the percentage of employees with deductible levels between \$100-\$500/ \$500-\$1000/ \$1000-\$2500/ >\$2500, etc. This predictive model will output the probability that employers had deductibles in the three categories (summing to 1) and we will assign the employer to the level that had the highest probability. If we detect employers that had 10 or more employees with whole number deductible levels both above and below \$500 (e.g. \$250.00 and \$1500.00), we will assign the employers' category as "choice." If 100% of employees had Health Savings Accounts, we will overwrite any previous assignment to classify the employer as a high-deductible employer. We will test the predictive model on the other half of the sample for which we have actual deductible levels. At employers with 75-100 workers, we anticipate to find sensitivity and a specificity of over 96%. We will have all study years (2004-2014) available in-house. The sample size (see section C.10) will be sufficient to investigate HDHPs' effects within carefully selected employer groups, as well as within vulnerable patient subgroups.

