
Our patient partner, DBSA, will help recruit **Aim 4 interview respondents** through local chapter meetings and social media platforms. Interested individuals will contact DBSA, who will screen for eligibility. Participants will be non-elderly adult patients with bipolar illness enrolled in commercial plans or caretaking family members, able to converse in English; respondents will give informed consent for recorded telephone interviews of approximately 1 hour, each conducted using a semi-structured interview guide.

C.3 Interventions and Comparators [RQ-5; HT-1 to HT-4]: Our analyses in **Aims 1-3** will include members of traditional health plans (including low-deductible Health Maintenance Organization, Preferred Provider Organization, and Point of Service plans) and HDHPs. We define traditional health plans as those having annual deductibles of \$500 or less for individuals and copayments of less than \$50 for most services. We

[name]

define HDHPs as those requiring individuals to spend at least \$1000 out-of-pocket annually for most clinical services before more comprehensive coverage begins, but which typically have exemptions for preventive care.

[figure not shown]
We will further classify HDHPs as HSA-eligible and HSA-ineligible. HSA-eligible HDHPs subject most medical services (including psychotropic medications and all mental health visits) to the annual deductible; only “preventive” health care (a limited set of services such as check-ups and screenings) are under first-dollar coverage, either for free or with a modest copayment. By contrast, HSA-ineligible HDHPs also subject many services to the deductible, but they generally include more generous coverage for medications (i.e., tiered copayments, as in traditional plans) and primary care visits might require only a modest copayment. These coverage differences for key services create a natural experiment that will permit us to answer crucial questions regarding optimal insurance designs for patients with bipolar illness.

For **Aim 4** in-depth interviews, we will sample respondents with either traditional insurance or HDHPs in order to explore this contrast. However, we recognize that many respondents may not fully understand the design of their insurance plan, and we expect new themes to emerge regarding lack of benefits clarity.

C.4 Enrollment Period and Follow-up Duration for Aims 1-3:

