C.9 Analysis Plan for Aims 1-3 [IR-3; HT-1 to HT-4]: Overview: These analyses will determine how specific outcomes change after employer-mandated switching from traditional plans to HDHPs. To address methodological standard IR-3, we plan to use the most rigorous quasi-experimental retrospective longitudinal designs and analyses available for AIMS 1-3, namely interrupted time series with comparison series matched on multiple baseline covariates as well as the baseline trend of outcome measures. For Aim 4 we will use appropriate standard techniques for qualitative analyses of interview data (detailed below). We will first compare the characteristics of our matched cohorts (HSA-eligible and HSA-ineligible HDHP members, and traditional plan controls) using chi-square tests, t-tests and Poisson or quantile regression.¹²⁶ We will contrast sociodemographic characteristics, employer characteristics, and baseline health care utilization. Subsequent analyses will use time-series plots and rigorous analytical methods appropriate for each outcome, described below. Data collected on the same individuals in successive years are correlated (“repeated observations”). The extended general linear models—generalized estimating equations (GEE) and generalized linear mixed models (GLMM) for binary, count, or continuous measured outcomes—are appropriate methods for estimating parameters to adjust for these correlations within subjects.^{82,83} The term of interest in our GEE or GLMM models will be the interaction between *time* (pre versus post) and *cohort* (HDHP versus traditional plan). Statistical analyses in Aims 1-3 will first compare those transitioning to HDHPs with patients remaining in traditional plans; then contrast effects between HDHP members with full drug cost-sharing (HSA-eligible plans) and those transitioning to HDHPs without full drug cost-sharing (HSA-ineligible HDHPs). Each HDHP group will have as controls only those traditional plan members paired to a given HDHP member during the propensity score match. To examine possible selection effects due to applying our enrollment criteria and propensity matching approaches (see C.10), we will also compare our analytic population to members with bipolar disorder who were excluded from the sample.^[MD-4; CI-2]

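### The HSA-eligible versus HSA-ineligible contrast is labelled as a drug cost-sharing effect, but the two plan types may also differ in primary care and specialist visit coverage and in deductible size, and nothing in the plan separates these features

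*Combined protocol and SAP*

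**What the plan says.** The second comparison in C.9 (Overview) is to "contrast effects between HDHP members with full drug cost-sharing (HSA-eligible plans) and those transitioning to HDHPs without full drug cost-sharing". The two groups are named by their drug benefit. C.5 builds the cohorts the same way: HSA-eligible plans with full drug cost-sharing, or HSA-ineligible plans with drug copayments as in traditional plans.

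The plan describes the rest of the benefit in two places.

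- C.3: "HSA-eligible HDHPs subject most medical services (including psychotropic medications and all mental health visits) to the annual deductible". For HSA-ineligible plans it notes the more generous drug coverage and adds that "primary care visits might require only a modest copayment".
- A.3: HSA-ineligible plans generally have more generous drug coverage "and specialist visits might be exempt from the deductible; most other services including mental health visits and hospitalizations are subject to the deductible". A.3 also says that plans linked to an HSA have a regulated structure with minimum deductible amounts.

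The intended use is stated in B.3: "Evidence that exempting mood stabilizing drugs from full cost-sharing preserves appropriate utilization" could contribute to amending the 2003 Act. F.2 gives, as an example of a finding to take to policymakers, that generous drug coverage within HDHPs protects patients. F.3 bases the contrast of two built-in interventions on drug coverage alone.

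C.2 lists the benefit data held for about 80% of employers, "including individual and family deductible levels, HDHP type (HSA, Health Reimbursement Arrangement, or non-account), and copay and coinsurance amount by service type".

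**The concern.** Suppose drug benefits were classified without error and members were perfectly balanced at baseline. The two HDHP groups could still differ in what a primary care or specialist visit costs and in how large the deductible is. These features change at the same switch as the drug benefit. The contrast then estimates the effect of one package against another.

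This matters most directly for the Aim 1 counts of primary care visits, whose price may itself differ between the groups, and for total out-of-pocket cost in Aim 3. It matters less directly for adherence, since prescriptions need contact with a prescriber, and for the acute-care outcomes of Aim 2. What is at stake is the policy inference. A package difference would not show that exempting drugs alone, with everything else unchanged, produces the result.

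**Working it through.** The plan states no figure for this point, so the check is of the text, followed by one identity.

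**1. Which features differ, as described**

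| Feature | HSA-eligible | HSA-ineligible | Stated difference? |
|---|---|---|---|
| Drugs | under the deductible (A.3, C.3) | copayments (C.3, C.5) | yes |
| Primary care visits other than preventive care | under the deductible (A.3, C.3) | possibly a modest copayment (C.3) | possible |
| Specialist visits | under the deductible (A.3) | possibly exempt (A.3) | possible |
| Mental health visits | under the deductible (A.3, C.3) | under the deductible (A.3) | no |
| Deductible size | regulated minimum (A.3) | no such rule described | possible, by inference only |

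C.3 applies one threshold of at least $1000 per individual to all HDHPs. That sets a common floor but does not make the deductibles equal.

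**2. Whether any step isolates the drug benefit**

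- Arm definition (C.5): fixed by drug coverage; visit coverage is left free.
- Employer propensity score (C.6): models switching to any HDHP versus staying in a traditional plan. It does not model HSA versus non-HSA.
- Covariates (C.8): employer and member characteristics; no term for the benefit design after the switch.
- Models (C.9): time, period, cohort, their interactions and patient covariates; no benefit-design term.
- Controls (C.9): each HDHP group keeps its own matched traditional-plan members. This removes shared trends and baseline differences. It cannot remove a visit benefit or deductible that changes in the same index month as the drug benefit.
- Imputation (C.2): for employers without benefit detail, the algorithm returns one of three deductible classes. The top class holds everything above $1000, so it says nothing about visit cost-sharing or about deductible size among HDHPs.
- Limitations (second section numbered C.11): untracked account balances are discussed; this bundling is not.

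**3. What the contrast then estimates**

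Write the HSA-ineligible minus HSA-eligible difference in effects as

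contrast = D + q × V + S

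Here D is the effect of the drug benefit. q is the share of HSA-ineligible members whose primary care or specialist visits fall outside the deductible, and V is the effect of that coverage on the outcome. S is the effect of any difference in deductible size. The effects are taken to be additive. The plan would read the whole sum as D, so the error is q × V + S.

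The documents give no value for q, V or S. As an assumption only, with S = 0, q from 0.25 to 1 and V from 0.5 to 2 percentage points:

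- low end: 0.25 × 0.5 = 0.125 points
- high end: 1 × 2 = 2 points
- q = 0 or V = 0: no error

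**The case against.** The best defence has four parts.

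First, the package difference is disclosed. C.3 speaks of coverage differences in the plural, and the opening of section C describes two types of HDHP with distinct benefit structures. On this view only the short label is at fault. That is true of the description, but the label carries into the cohort definition, the contrast and the intended policy use, and no analysis step takes up the disclosed differences.

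Second, the visit differences are hedged. A reader might infer that a visit effect certainly will be credited to drugs, or that mental health visits are cheaper in HSA-ineligible plans. The documents support neither. Both visit statements express a possibility, and A.3 puts mental health visits under the deductible in HSA-ineligible plans too. This weakens the prescriber-access route to an adherence effect, because mental health visits are the ones most relevant to bipolar disorder. A difference in deductible size is likewise only an inference from the regulated HSA minimum.

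Third, B.3 and F.2 are conditional statements about how evidence could be used. They are not conclusions or recommendations to change the law, and should not be read as such. They still show how a difference would be interpreted.

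Fourth, C.7 measures visits separately from adherence and sums costs separately for fills and visits, so a visit response would be visible. That stands, but seeing a visit response does not divide an adherence or hospitalization effect into its parts.

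**Conclusion.** The point holds as one of interpretation. As planned, the contrast compares two plan packages and is labelled as the effect of drug cost-sharing. Any effect of primary care coverage, specialist coverage or deductible size would be counted as an effect of drug coverage.

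Its size cannot be derived from the documents. It depends on how often the features differ and how much they matter, and it is zero if they do not differ. A reader might try to express it as a share of the 6% relative adherence decrease in C.10. That figure is a detectable change for the HSA cohort, not an HSA versus non-HSA difference, so no share follows from it.

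The comparison of HDHPs with traditional plans is unaffected, since it concerns the switch to an HDHP as a whole. The plan should be changed because the remedy is cheap and bears on what the study can say about drug exemptions.

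**What to change.** 1. Among employers with benefit detail (about 80%, C.2), tabulate deductible level and primary care and specialist copayment and coinsurance by HDHP type before the outcome analyses of this contrast.
2. Add an analysis of the contrast restricted to, or matched within, employers with comparable deductible bands and comparable visit cost-sharing.
3. C.2 does not list a field showing whether a service is exempt from the deductible. If the fields held cannot show this, or if overlap is too thin, report the result as HSA-eligible versus HSA-ineligible plan package, not as the effect of exempting drugs.
4. In that case, align B.3, F.2, F.3 and the wording of C.9, and add the bundling to the limitations.

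Cost: employers without benefit detail, and HSA-ineligible employers with non-comparable benefits, drop out of this analysis. The share of members lost is not stated, and 80% of employers need not mean 80% of members.

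For illustration, start from the 1525 HSA and 9275 non-HSA members in C.10. Assume that 80% of members remain in each group, that all remaining HSA members are usable, and that a share s of the remaining HSA-ineligible members is comparable. Ignore clustering. The standard error is proportional to √(1/n₁ + 1/n₂). The 1:4 matched controls scale both terms equally, so the ratios are unchanged.

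- Full sample: √(1/1525 + 1/9275) = 0.0276
- s = 1: 1220 and 7420, 0.0309, about 12% wider
- s = 0.5: 1220 and 3710, 0.0330, about 19% wider
- s = 0.25: 1220 and 1855, 0.0369, about 33% wider

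The full-sample contrast can still be reported beside it as the package comparison. Rewording alone needs no new data.
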